## 9.4.4 Safety Analyses

Safety will be evaluated throughout study participation in order to assess symptomology and the development of adverse events. AEs will be tracked in CRFs and reported in compliance with Policy 801.

#### 9.4.5 Baseline Descriptive Statistics

The demographic composition of the sample, including sex assigned at birth, gender identity, race, ethnicity, age, markers of socioeconomic status, and BMI will be tabulated for the full sample in order to aid interpretation of the generalizability of the sample. Because the sequence groups are randomized, inferential tests of baseline differences are inappropriate.

### 9.4.6 Tabulation of individual Participant Data

Individual participant data will not be listed; only summary statistics will be presented.

## 9.4.7 Exploratory Analyses

We will conduct primary and secondary analyses as specified in Sections 9.4.2 and 9.4.3. We will not conduct exploratory analysis for confirmatory proof for registration trials.

#### 10 REGULATORY AND OPERATIONAL CONSIDERATIONS

#### 10.1 INFORMED CONSENT PROCESS

#### 10.1.1 Consent/Assent Procedures and Documentation

All participants will receive a verbal explanation in terms suited to their comprehension of the purposes, procedures and potential risks of the study and of their rights as research participants. In-person consent will be obtained at the NIH CC (see below for telephone and telehealth consent processes). Participants will be provided as much time as is required to carefully review the written consent form and ask questions of consenting investigators regarding this study prior to signing.

Consent will be obtained by authorized licensed independent practitioners with patient care and clinical research privileges in the NIH CC. All those study investigators obtaining informed consent have completed the NIMH HSPU 'Elements of Successful Informed Consent' training.

An HSPU team member will monitor the informed consent process for patients, which may then, in certain circumstances, trigger the need for a formal independent capacity assessment. Subjects without consent capacity excluded from participation.

## 10.1.2 For assent of children, if applicable

This section is not applicable.

## 10.1.3 Consent for minors when they reach the age of majority

This section is not applicable.

## **10.1.4** Telephone and Telehealth Consent

The informed consent document will be sent to the subject. An explanation of the study will be provided over the telephone after the subject has had the opportunity to read the consent form. The subject will sign and date the informed consent. The original informed consent document will be sent back to the consenting investigator who will sign and date the consent form with the date the consent was returned. A fully executed copy will be returned via mail for the subject's records. The informed consent process will be documented on a progress note by the consenting investigator. The investigator will confirm that, when required, written legally effective consent has been obtained prior to initiating any study interventions.

Sometimes it is necessary to obtain information about symptoms by electronic media, obtain measures of symptom severity, or conduct other eligible procedures (e.g. interviews, questionnaires, and psychological testing) by telehealth. Under such circumstances, this process will be utilized to obtain telehealth consent for this study using NIH-approved platforms.

## 10.1.5 Telephone Assent

This section is not applicable.

## 10.1.6 Consent of subjects who are or become, decisionally impaired

Adults unable to provide consent are excluded from enrolling in the protocol. However, it is possible that subjects enrolled in the protocol may permanently lose the capacity to consent for

themselves during the course of this study. In the event this occurs, the subjects will be withdrawn from the study.

## 10.1.7 Considerations for Consent of NIH staff, or family members of study team members

Consent for NIH staff will be obtained as detailed above with following additional protections:

Consent from staff members will be obtained by an individual independent of the staff member's team whenever possible. Otherwise, the consent procedure will be independently monitored by the CC Department of Bioethics Consultation Service in order to minimize the risk of undue pressure on the staff member.

#### 10.2 STUDY DISCONTINUATION AND CLOSURE

This study may be temporarily suspended or prematurely terminated if there is sufficient reasonable cause. Written notification, documenting the reason for study suspension or termination, will be provided by the suspending or terminating party to study participants, investigator, funding agency, and regulatory authorities. If the study is prematurely terminated or suspended, the PI will promptly inform study participants, the IRB, and sponsor and will provide the reason(s) for the termination or suspension. Study participants will be contacted, as applicable, and be informed of changes to study visit schedule.

Circumstances that may warrant termination or suspension include, but are not limited to:

- Determination of unexpected, significant, or unacceptable risk to participants
- Demonstration of efficacy that would warrant stopping
- Insufficient compliance to protocol requirements
- Data that are not sufficiently complete and/or evaluable
- Determination that the primary endpoint has been met
- Determination of futility

Study may resume once concerns about safety, protocol compliance, and data quality are addressed, and satisfy the sponsor, IRB and, as applicable, the FDA.

#### 10.3 CONFIDENTIALITY AND PRIVACY

Participant confidentiality and privacy are strictly held in trust by the participating investigators, their staff, and the sponsor. This confidentiality is extended to cover testing of biological samples and genetic tests in addition to the clinical information relating to participants. Therefore, the study protocol, documentation, data, and all other information generated will be held in strict confidence. No information concerning the study or the data will be released to any unauthorized third party without prior written approval of the sponsor.

This study collects sensitive information, including personal and family medical and treatment history. The PI will train study staff regarding obtaining and handling potentially sensitive and private information about NIH employees and staff through staff discussions and written branch/section procedures.

Hard copy research data/records will be coded, no individual will be identified by name, and the data will be stored in a locked filing cabinet stored in locked offices maintained by the PI to

protect subject anonymity. Electronic data with identifiers will be saved on NIH secured servers. Data will be kept in password-protected computers. Samples will be kept in locked storage.

Samples and data will be stored using codes that we assign. Only study investigators and clinical monitors will have access to the samples and data with patient identifiable information (PII). Offsite associate investigators will not have access to PII.

The study monitor, other authorized representatives of the sponsor, representatives of the IRB, and/or regulatory agencies may inspect all documents and records required to be maintained by the investigator, including but not limited to, medical records (office, clinic, or hospital) and pharmacy records for the participants in this study. The clinical study site will permit access to such records.

The study participant's contact information will be securely stored for internal use during the study. At the end of the study, all records will continue to be kept in a secure location for as long a period as dictated by the reviewing IRB, Institutional policies, or sponsor requirements.

Study participant research data, which is for purposes of statistical analysis and scientific reporting, will be transmitted to and stored at the Clinical Trials Database (CTDB) at NIH. This will not include the participant's contact or identifying information. Rather, individual participants and their research data will be identified by a unique study identification number. The study data entry and study management systems used by clinical sites and by ETPB/NIMH research staff will be secured and password protected. At the end of the study, all study databases will be de-identified and archived at the CTDB.

To further protect the privacy of study participants, a Certificate of Confidentiality has been issued by the NIH. This certificate protects identifiable research information from forced disclosure. It allows the investigator and others who have access to research records to refuse to disclose identifying information on research participation in any civil, criminal, administrative, legislative, or other proceeding, whether at the federal, state, or local level. By protecting researchers and institutions from being compelled to disclose information that would identify research participants, Certificates of Confidentiality help achieve the research objectives and promote participation in studies by helping assure confidentiality and privacy to participants.

#### 10.4 FUTURE USE OF STORED SPECIMENS AND DATA

Biological samples will be kept in freezers by the NIMH/ETPB with no patient identifiers. Information on processing and storage of samples is on record with the Clinical and Scientific Director's offices at the NIMH. Samples will be collected, handled, stored, and shipped as outlined in the Data Handling and Record Keeping section. Results will be published as group data without the use of characteristics that would identify individual subjects. Samples and date will be stored using codes that we assign. Only study investigators will have access to the stored samples.

#### 10.5 SAFETY OVERSIGHT

This protocol will be reviewed by the NIMH-IRP Data and Safety Monitoring Board. The DSMB meets two times per year. The board will review study accrual and progress, adverse events related to the study, and safety and outcome data. Specific data elements required by the DSMB will be established at the first meeting the protocol is reviewed. The DSMB will have the authority to require changes in the study design, or to stop all or part of any study based on accumulating safety data.

The medically responsible investigator has the authority to break the blind in the event of an emergency. Breaking of the blind, life threatening injury or death all require immediate reporting to the DSMB and the NIMH Clinical Director. A written notification to the DSMB chair must follow within 7 days.

#### 10.6 CLINICAL MONITORING

Details of clinical site monitoring are documented in a Clinical Monitoring Plan (CMP). The CMP describes in detail who will conduct the monitoring, at what frequency monitoring will be done, at what level of detail monitoring will be performed, and the distribution of monitoring reports.

As per ICH-GCP 5.18 and FDA 21 CFR 312.50 clinical protocols are required to be adequately monitored. Monitoring for the NIH site will be conducted according to the "NIMH Intramural Program Guidelines for Monitoring of Clinical Trials". Monitors under contract to the NIMH OCD ORO will visit the NIH site to monitor aspects of the study in accordance with the appropriate regulations and the approved protocol. The objectives of a monitoring visit will be: 1) to verify the existence of signed informed consent documents and documentation of the ICF process for each monitored subject; 2) to verify the prompt and accurate recording of all monitored data points, and prompt reporting of all SAEs; 3) to compare abstracted information from clinical databases (e.g. CTDB) with individual subjects' records and source documents (subjects' charts, laboratory analyses and test results, physicians' progress notes, nurses' notes, and any other relevant original subject information); and 4) to help ensure investigators are in compliance with the protocol. The monitors also will inspect the clinical site regulatory files to ensure that regulatory requirements (Office for Human Research Protections-OHRP), FDA, and applicable guidelines (ICH-GCP) are being followed. During the monitoring visits, the investigator (and/or designee) and other study personnel will be available to discuss the study progress and monitoring visit.

The investigator (and/or designee) will make study documents (e.g., consent forms, clinical database records and pertinent hospital/sources or clinical records) readily available for inspection by the local IRB, FDA, the site monitors, and the NIMH staff for confirmation of the study data.

A specific protocol monitoring plan will be discussed with the Principal Investigator and study staff. The plan will outline the frequency of monitoring visits based on such factors as study enrollment, data collection status and regulatory obligations.

## 10.7 QUALITY ASSURANCE AND QUALITY CONTROL

Each clinical site will perform internal quality management of study conduct, data and biological specimen collection, documentation and completion. An individualized quality management plan will be developed to describe a site's quality management.

Quality control (QC) procedures will be implemented beginning with the data entry system and data QC checks that will be run on the database will be generated. Any missing data or data anomalies will be communicated to the site(s) for clarification/resolution.

Following written Standard Operating Procedures (SOPs), the monitors will verify that the clinical trial is conducted and data are generated and biological specimens are collected, documented (recorded), and reported in compliance with the protocol, International Conference

on Harmonisation Good Clinical Practice (ICH GCP), and applicable regulatory requirements (e.g., Good Laboratory Practices (GLP), Good Manufacturing Practices (GMP)).

The investigational site will provide direct access to all trial related sites, source data/documents, and reports for the purpose of monitoring and auditing by the sponsor, and inspection by local and regulatory authorities.

#### 10.8 DATA HANDLING AND RECORD KEEPING

## 10.8.1 Data Collection and Management Responsibilities

Data collection is the responsibility of the clinical trial staff at the site under the supervision of the site investigator. The investigator is responsible for ensuring the accuracy, completeness, legibility, and timeliness of the data reported.

All source documents should be completed in a neat, legible manner to ensure accurate interpretation of data.

Hardcopies of the study visit worksheets will be provided for use as source document worksheets for recording data for each participant enrolled in the study. Data recorded in the electronic case report form (eCRF) derived from source documents should be consistent with the data recorded on the source documents.

Clinical data (including demographics information, clinical rating scales, and AEs) and clinical laboratory data will be recorded in paper form or entered into CTDB, a 21 CFR Part 11-compliant data capture system provided by the NICHD. The data system includes password protection and internal quality checks, such as automatic range checks, to identify data that appear inconsistent, incomplete, or inaccurate. Clinical data will be entered directly or from the source documents.

Electronic data (including imaging data) and electronic personally-identifiable health information (ePHI) will be stored on secure servers within the NIH firewall with access for study personnel only.

## 10.8.2 Study Records Retention

Study documents should be retained for a minimum of 2 years after the last approval of a marketing application in an International Conference on Harmonisation (ICH) region and until there are no pending or contemplated marketing applications in an ICH region or until at least 2 years have elapsed since the formal discontinuation of clinical development of the study intervention, and as per the NIH Intramural Records Retention Schedule. No records will be destroyed without the written consent of the sponsor, if applicable. It is the responsibility of the sponsor to inform the investigator when these documents no longer need to be retained.

#### 10.9 PROTOCOL DEVIATIONS

It is the responsibility of the investigator to use continuous vigilance to identify and report deviations to the NIH Institutional Review Board as per Policy 801. All deviations must be addressed in study source documents, reported to the NIMH Program Official and Office of the Clinical Director. The investigator is responsible for knowing and adhering to the reviewing IRB requirements.

#### 10.9.1 NIH Definition of Protocol Deviation

A protocol deviation is any changed, divergence, or departure from the IRB-approved research protocol.

- Major deviations: Deviations from the IRB approved protocol that have, or may have the potential to, negatively impact the rights, welfare or safety of the subject, or to substantially negatively impact the scientific integrity or validity of the study.
- Minor deviations: Deviations that do not have the potential to negatively impact the rights, safety or welfare of subjects or others, or the scientific integrity or validity of the study.

#### 10.10 PUBLICATION AND DATA SHARING POLICY

## 10.10.1 Human Data Sharing Plan

This study will be conducted in accordance with the following publication and data sharing policies and regulations:

National Institutes of Health (NIH) Public Access Policy, which ensures that the public has access to the published results of NIH funded research. It requires scientists to submit final peer-reviewed journal manuscripts that arise from NIH funds to the digital archive PubMed Central upon acceptance for publication.

This study will comply with the NIH Data Sharing Policy and Policy on the Dissemination of NIH-Funded Clinical Trial Information and the Clinical Trials Registration and Results Information Submission rule. As such, this trial will be registered at ClinicalTrials.gov, and results information from this trial will be submitted to ClinicalTrials.gov. In addition, every attempt will be made to publish results in peer-reviewed journals. Data from this study may be requested from other researchers 6 years after the completion of the primary endpoint by contacting the ETPB.

## 10.10.2 Genomic Data Sharing Plan

This study will comply with the NIH Genomic Data Sharing Policy, which applies to all NIH-funded research that generates large-scale human or non-human genomic data, as well as the use of these data for subsequent research. Large-scale data include genome-wide association studies (GWAS), single nucleotide polymorphisms (SNP) arrays, and genome sequence, transcriptomic, epigenomic, and gene expression data.

#### 10.11 COLLABORATIVE AGREEMENTS

## 10.11.1 Agreement Type

A CRADA was established between the NIMH and Taisho Pharmaceutical Co., Ltd. Taisho Pharmaceutical Co., Ltd. will manufacture the study drug and placebo for this protocol. NIMH will be responsible for obtaining the IND, subject recruitment, clinical care, conduct of the research study and procedures, study monitoring, analyzing and writing, and publishing study results.

#### 10.12 CONFLICT OF INTEREST POLICY

The independence of this study from any actual or perceived influence, such as by the pharmaceutical industry, is critical. Therefore, any actual conflict of interest of persons who have a role in the design, conduct, analysis, publication, or any aspect of this trial will be disclosed and

managed. Furthermore, persons who have a perceived conflict of interest will be required to have such conflicts managed in a way that is appropriate to their participation in the design and conduct of this trial. The study leadership in conjunction with the NIMH has established policies and procedures for all study group members to disclose all conflicts of interest and will establish a mechanism for the management of all reported dualities of interest.

## 11 ABBREVIATIONS

AMPA	α-Amino-3-Hydroxy-5-Methyl-4-Isoxazolepropionic Acid
ANCOVA	Analysis of Covariance
ATHF	Antidepressant Treatment History Form
BBB	Blood Brain Barrier
BCRP	Breast Cancer Resistance Protein
BDNF	Brain Derived Neurotrophic Factor
BLS	Basic Life Support
BMI	Body Mass Index
BOLD	Blood Oxygenation Level Dependent
BPRS	Brief Psychiatric Rating Scale
CADSS	Clinician-Administered Dissociative States Scale
CAMKIII	Calcium-Calmodulin Dependent Protein Kinase III
CBC	Complete Blood Count
CES	Carboxylesterase
CLIA	Clinical Laboratory Improvements Amendments
Cmax	Maximum plasma concentration
CMP	Clinical Monitoring Plan
COC	Certificate of Confidentiality
COVID-19	Coronavirus Disease 2019
COWAT	Controlled Oral Word Association Test
CPT 3	Conners Continuous Performance Test 3rd Edition
CRA	Clinical Research Advocate
CRP	C-Reactive Protein
CSF	Cerebrospinal Fluid
C-SSRS	Columbia-Suicide Severity Rating Scale
CTDB	Clinical Trials Database
CVLT-II	California Verbal Learning Test - Second Edition
CYP	Cytochrome P-450

dbGap	database of Genotypes and Phenotypes
DSST	Digit Symbol Substitution Test
D-KEFS	Delis-Kaplan Executive Function System
DRTS	Designation of Reimbursement for Travel and Subsistence
ECG	Electrocardiogram
ECT	Electroconvulsive therapy
eEF2K	eukaryotic Elongation Factor-2 Kinase
ePHI	electronic Personally-Identifiable Health Information
FDA	Food and Drug Administration
fMRI	functional Magnetic Resonance Imaging
FST	Forced Swim Test
GDNF	Glial-Derived Neurotrophic Factor
HAM-A	Hamilton Anxiety Rating Scale
HCG	Human Chorionic Gonadotropin
HDRS	Hamilton Depression Rating Scale
HIV	Human Immunodeficiency Virus
HNK	Hydroxynorketamine
HSPU	Human Subjects Protection Unit
HVLT-R	Hopkins Verbal Learning Test - Revised
IDMRS	Investigational Drug Management and Research Section
IEC	International Electrotechnical Commission
IFN	Interferon
IGF-1	Insulin-like Growth Factor-1
IL	Interleukin
ISM	Independent Safety Monitor
ISO	International Organization for Standardization
ITT	Intent-To-Treat
LPS	Lipopolysaccharide
MAD	Multiple Ascending Dose
MADRS	Montgomery-Asberg Depression Rating Scale
MAOI	Monoamine Oxidase Inhibitor
MDD	Major Depressive Disorder
MDEs	Major Depressive Episodes
MEG	Magnetoencephalography
mGlu	metabotropic Glutamate

mPFC	medial Prefrontal Cortex			
mRNA	Messenger Ribonucleic Acid			
MRS	Magnetic Resonance Spectroscopy			
mTORC1	mammalian Target of Rapamycin			
NIH	National Institutes of Health			
NMDAR	N-Methyl-D-Aspartate Receptor			
NO	Nitric Oxide			
NOAEL	No Observed Adverse Effect Level			
NSR	Non-Significant Risk			
OAT3	Organic Anion Transporter 3			
OATP1B1	Organic Anion Transporting Polypeptide 1B1			
OHRP	Office for Human Research Protections			
PANAS	Positive and Negative Affect Schedule			
PBMC	Peripheral Blood Mononuclear Cell			
PCR	Polymerase Chain Reaction			
PFC	Prefrontal Cortex			
PI	Principal Investigator			
PII	Personally Identifiable Information			
POC	Proof-of-Concept			
PRN	Pro Re Nata			
RAVLT	Rey Auditory Verbal Learning Test			
RDoC	Research Domain Criteria			
RF	Radio Frequency			
RH	Relative Humidity			
SAD	Single-Ascending Dose			
SCID-P	Structured Diagnostic Interview-Patient Version			
SHAPS	Snaith Hamilton Pleasure Scale			
SNP	Single Nucleotide Polymorphism			
SOC	System Organ Class			
SOP	Standard Operating Procedure			
SSI	Scale for Suicidal Ideation			
SWA	Slow-Wave sleep Activity			
TEPS	Temporal Experience of Pleasure Scale			
TMS	Transcranial Magnetic Stimulation			
TRD	Treatment Resistant Depression			

TrkB	Tropomyosin-Related Kinase B
TS-161	TP0473292
TSH	Thyroid Stimulating Hormone
TTX	Tetradotoxin
VEGF	Vascular Endothelial Growth Factor
YMRS	Young Mania Rating Scale

## 13 APPENDICES

## 13.1 APPENDIX A. FIVE QUESTION CONSENT QUIZ

TS-161 is not an FDA-approved for major depressive disorder (MDD).	True	False
You will receive a placebo during this study.	True	False
If you are able to get pregnant, you will have a pregnancy test before taking TS-161. There may be birth defects with TS-161.	True	False
We will look at chemicals in the brain and how they respond to TS-161.	True	False
You may not get any benefit from participating in this study.	True	False

Note: Correct responses are highlighted for this document

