#### 2.3.2 Known Potential Benefits

This study offers no direct benefits to participants but is likely to yield important and generalizable knowledge about the development of new treatments for MDD.

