#### 4 STUDY DESIGN

#### 4.1 OVERALL DESIGN

This is a Phase 2 randomized, double blind, placebo-controlled, crossover, single—site, approximately 16-week inpatient experimental study that will assess the efficacy and safety of three weeks of 50 to 100 mg/day of TS-161, an mGlu2/3 receptor antagonist prodrug. Subjects will meet diagnostic criteria for MDD without psychotic features, according to DSM-IV or DSM-5 guidelines and confirmed by the SCID-P. Approximately 25 subjects with MDD will be recruited for this study to allow 20 subjects to crossover and complete the study. TS-161 and placebo will be taken orally in capsule form as a single daily dose for 3 weeks in each of two crossover Research Conditions.

This single site, inpatient study will be conducted at the NIH Clinical Center in Bethesda, MD. The protocol will not include interim analyses, substudies, or stratifications.

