## 5 STUDY POPULATION

## 5.1 INCLUSION CRITERIA

In order to be eligible to participate in this study, an individual must meet all of the following criteria:

- 1. Ability of subject to understand and the willingness to sign a written informed consent document. To verify this, subjects must score ≥ 80% on the consent quiz (Appendix A).
- 2. Stated willingness to comply with all study procedures and availability for the duration of the study.
- 3. Aged 18 to 65.
- 4. Subjects must fulfill DSM-IV or DSM-5 criteria for MDD, single episode or recurrent without psychotic features, based on clinical assessment and confirmed by a structured diagnostic interview (SCID-P). Subjects must be experiencing a current major depressive episode of at least 4 weeks duration.
- 5. Subjects must have an initial score of  $\geq$  20 on the MADRS and a YMRS score of  $\leq$  12 within one week of the start of Phase I and upon entry into Phase II.
- 6. Ability to take oral medication and be willing to adhere to the TS-161 regimen.
- 7. Subjects must have a current or past history of lack of response to at least one adequate antidepressant trial (may be from the same chemical class) in the current major depressive episode, operationally defined using the modified-Antidepressant Treatment History Form (ATHF)); a failed adequate trial of ECT [or TMS] would count as an adequate antidepressant trial.
- 8. For females of reproductive potential: use of contraception starting at the time of enrollment and agreement to use such a method during study participation and for an additional 4 weeks after the end of Phase II (see Contraception Guidance, Appendix D).
- 9. For males of reproductive potential: use of condoms or other methods from the time of enrollment to ensure effective contraception with partner, and for an additional 90 days after the end of Phase II (see Contraception Guidance, Appendix D).
- 10. Agreement to adhere to Lifestyle Considerations throughout study duration

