#### **6 STUDY INTERVENTION**

## 6.1 STUDY INTERVENTIONS(S) ADMINISTRATION

# 6.1.1 Study Intervention: TP0473292 (IND)

The use of TP0473292 (TS-161) in this study has been approved by the FDA under IND #153429. The study drug will be supplied by Taisho Pharmaceutical Co., Ltd. The sponsor of the IND is the National Institute of Mental Health. The IB is attached in iRIS.

TS-161 is not available for commercial use.

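### Every consent-quiz item appears to have True as its answer, so answering True throughout meets the 80% rule and the quiz cannot tell understanding from agreement

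*Combined protocol and SAP*

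**What the plan says.** Section 5.1, criterion 1, requires that a candidate can understand and is willing to sign the consent document. As verification it states that "subjects must score ≥ 80% on the consent quiz". The quiz in Appendix A (Section 13.1) has five statements, each answered True or False. They cover the drug's unapproved status, receipt of placebo, pregnancy testing together with possible birth defects, measurement of brain chemicals, and possible lack of benefit. The placebo item reads "You will receive a placebo during this study". A note under the quiz says "Correct responses are highlighted for this document", but the highlighting does not show in the text as supplied.

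Section 10.1.1 adds that a member of the Human Subjects Protection Unit (HSPU) monitors consent, which may lead to a formal independent capacity assessment. Section 2.3.1.2 assigns each patient a Clinical Research Advocate from initial consent to study completion.

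**The concern.** A True/False test with every answer on the same side can be passed by a candidate who simply agrees with each statement. Agreement is a plausible way for a patient to answer without understanding, and here it earns a pass.

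The quiz is the only scored check in criterion 1. The trial states more than minimal risk (Section 2.3.1) and no direct benefit (Section 2.3.2). It also involves a medication taper and a delay in treatment of up to 16 weeks (Section 2.3.1.3). Section 5.3.4 says the investigators want all participants to understand the consent process and the procedures. What is at stake is the quality of a participant-protection check. The primary endpoint, randomization and analysis do not depend on it.

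**Working it through.** **Step 1. Infer the key from the protocol.**

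| Item | Protocol source | Expected answer |
|---|---|---|
| 1. Not approved for MDD | Section 6.1.1: used under an IND; "TS-161 is not available for commercial use" | True |
| 2. Placebo will be received | Section 4.1: "TS-161 and placebo will be taken orally in capsule form as a single daily dose for 3 weeks in each of two crossover Research Conditions" | True by design |
| 3. Pregnancy test, and possible birth defects | Section 8.6.13: test within 24 hours before each condition; Section 5.3.2: safety in pregnancy unknown | True on both parts |
| 4. Brain chemicals are examined | Section 2.2.6: glutamate measured by MRS | True as a study aim |
| 5. There may be no benefit | Section 2.3.2: "This study offers no direct benefits to participants" | True |

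**Step 2. Pass mark.** 0.80 × 5 = 4, so 4 correct answers are needed.

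**Step 3. Score for answering True throughout.** With f items keyed False, the score is (5 − f)/5.

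- f = 0: 5/5 = 100%, pass
- f = 1: 4/5 = 80%, pass
- f = 2: 3/5 = 60%, fail

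The pass therefore holds unless two or more items are keyed False in the unseen highlighting.

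**Step 4. What the quiz does reject.** For random guessing, P(at least 4 of 5) = (5 + 1)/32 = 6/32 = 18.75%, so 81.25% fail. With all items keyed True, a candidate who answers False twice scores 3/5 = 60% and fails.

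**Step 5. Candidates who lean towards True.** Suppose all items are keyed True and each is answered True with probability p, regardless of content (p is an assumption). Then P(pass) = 5p⁴(1 − p) + p⁵.

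- p = 0.7: 52.8%
- p = 0.8: 73.7%
- p = 0.9: 91.9%

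**Step 6. The revised quiz.** Splitting item 3 gives six items, of which two are reworded so that False is correct. The 80% rule needs 0.80 × 6 = 4.8, so 5 correct.

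- All-True: 4/6 = 67%, fail
- All-False: 2/6 = 33%, fail
- Random guessing: (6 + 1)/64 = 7/64 = 10.9%, against 18.75% now
- Leaning towards True: P(pass) = p⁴(1 − p)² + 4p³(1 − p)³ + 2p⁵(1 − p). At p = 0.9 this is 0.0066 + 0.0029 + 0.1181 = 12.8%, against 91.9% now.

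**The case against.** A reader might infer that the quiz cannot detect lack of understanding at all, or that the threshold gives no protection. The documents do not support that. Most random guessers fail. Items 1 and 5 are negatively worded, so a candidate who believes the drug is approved and expects to benefit would answer False to both and fail. The gap is confined to uniform or near-uniform agreement, and the documents say nothing about how often that occurs.

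A reader might also take the 100% score as established, or all five statements as unconditionally true. Neither is secure. The key is inferred. Item 2 does not hold for a participant given TS-161 first who is still a responder after the extra washout week, because Sections 4.2 and 8.3 withdraw that participant before Research Condition 2. Nor does it hold for someone who leaves during a first TS-161 period. Item 4 rests on a procedure that Section 8.4.3 heads as optional. These points weaken the 100% figure but hardly the pass. Placebo is planned for every participant and item 4 describes an aim, so True remains the natural key for both. Two False keys would be needed to overturn the conclusion.

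Finally, the quiz does not stand alone. HSPU monitoring, a possible capacity assessment and the Clinical Research Advocate all bear on consent, and incapacity is addressed through them. This objection stands and limits the consequence. These safeguards are unscored, however, and criterion 1 names the quiz as its means of verification.

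**Conclusion.** The point holds in a limited form. On the protocol's own content the expected answer to each item is True, so a candidate who answers True throughout scores 5/5, or 4/5 if one item is keyed False, and meets criterion 1 in both cases. The quiz filters out guessers and candidates with two or more wrong answers, but it cannot separate understanding from agreement. The conclusion assumes that no more than one item is keyed False, which the sponsor can confirm at once from the highlighted original.

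Two smaller defects accompany it. Item 3 puts two statements under one answer, so a candidate who grasps only one part cannot be scored meaningfully. Item 2 does not match the withdrawal rule for sustained responders. The matter is minor: worth correcting because it is cheap and concerns consent, with no bearing on the trial's primary result.

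**What to change.** - Reword at least two items so that False is correct. For example, item 1 could state that TS-161 has FDA approval for MDD, and item 5 that the participant will benefit directly from taking part.
- Split item 3 into one statement on pregnancy testing and one on possible birth defects, giving six items.
- Keep the 80% rule and state it as 5 of 6.
- Reconcile the wording of item 2 with the sustained-responder rule in Sections 4.2 and 8.3, so that the quiz and the protocol describe the same course.

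The cost is a revised one-page appendix and IRB approval. A few candidates may need the study explained again before they pass. No design, endpoint or analysis text changes.
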